### Sample Size and Population

Medicare beneficiaries from claims data provided by each ACO will be included in the final outcome analysis if they meet all of the following criteria prior to the start of the intervention: a) they are seen by a clinician at a participating clinic as evidenced by one or more evaluation and management claims, b) they have continuous coverage in Medicare Parts A, B and D and no months of Part C (Medicare Advantage), and c) they have two or more claims with an ICD-10 diagnosis for Alzheimer's or Alzheimer's related dementia 30 days apart or 1 inpatient stay with a principal diagnosis of Alzheimer's. We anticipate a total of approximately 5,000 patients will be included in this final analysis across both ACOs.

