## **4 SELECTION AND ENROLLMENT OF PARTICIPANTS**

### **4.1 Inclusion Criteria**

Clinician practices within two ACOs will be eligible for participation in the study if they meet the following criteria:

- a. They include 3 or more primary care providers (defined as a primary care physician (specialty code of 08 or 11), nurse practitioner (specialty code = 50) or physician's assistant (specialty code = 97)) and
- b. They have clinical encounters with 10 or more Medicare beneficiaries with Alzheimer's or Alzheimer's related dementia in the base years (2019-2020).

Medicare beneficiaries will be included in the study if they meet all of the following criteria during the intervention year:

- a. They are seen by a clinician at a participating practice as evidenced by one or more evaluation and management claim,
- b. They have continuous coverage in Medicare Parts A, B and D and no months of Part C (Medicare Advantage),
- c. They have two or more claims with an ICD-10 diagnosis for Alzheimer's or Alzheimer's related dementia 30 days apart or 1 inpatient stay with a principal diagnosis of Alzheimer's.

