### **9.2 Sample Size and Randomization**

Our sampling plan anticipates enrolling at least 30 of the 39 practices in USMM and 26 of the 28 practices in Ochsner. Based on Medicare enrollments of 39,000 members in USMM with a 20 percent dementia rate in 2019, and 10,000 members in Ochsner with approximately 10 percent of members diagnosed with dementia in 2019, we should have

at least 2,000 patients per treatment group for USMM and 500 patients per treatment group for Ochsner. For our primary outcome, with a follow-up period of one year and with mediation possession rates calculated per patient each quarter, we will have approximately 4 MPR observations per patient or 8,000 observations per group for USMM analyses and 2,000 per group for Ochsner. Even after assuming significant correlation across time within patient and modest correlation between patients within a practice, which will reduce effective sample sizes by 20%, we should have the equivalent of 6,400 observations per treatment group for our USMM analyses and 1,600 observations per treatment group for Ochsner.

The expectation of our intervention is that for each medication class, it will produce clinically relevant decreases in mean possession rates of 10% of a standard deviation. If the effect size is this large for a medication class and using a 5% level of significance, our Ochsner sample (with effective size of at least 1,600 per group) will have 80% power to discern a significant difference, while our larger USMM sample (with effective size of at least 6,400 per group) will have almost 100% power. Indeed, our USMM sample will have 80% power to find a significant difference, even if the effect size is only 5% of a standard deviation

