#### 9.2.1 Treatment Assignment Procedures

The unit of randomization will be the primary care practice or team. We anticipate 32 out of 39 teams from USMM to meet eligibility and 26 out of 28 practices for Ochsner. Within each ACO, we will randomly select half of the practices for participation in the value champion training and the remaining practices will continue with care as usual. Prior to random assignment, we will stratify practices based on high versus low historic prescribing rates. We will select practices for randomization and inclusion using a cut-point based on the distribution of overall rates for all 3 therapeutic classes using data for 2019-2020. Once randomized, a clinician value champion will be recruited from each of the clinics randomized to the intervention arm of the study in partnership with the ACO leadership.

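### The single 20% deduction for correlation in section 9.2 is too small for the correlations it describes, so the two stated 80% powers are unsupported

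*Combined protocol and SAP*

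**What the plan says.** Section 9.2 plans on 2,000 patients per group in USMM and 500 in Ochsner. Four quarterly MPRs per patient make 8,000 and 2,000 observations per group. It then allows for "significant correlation across time within patient and modest correlation between patients within a practice, which will reduce effective sample sizes by 20" percent, leaving 6,400 and 1,600.

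Power is computed on those reduced figures, "using a 5% level of significance". For a difference of 0.10 SD, "our Ochsner sample (with effective size of at least 1,600 per group) will have 80% power to discern a significant difference", and USMM is said to have almost 100%. For a smaller difference, "our USMM sample will have 80% power to find a significant difference, even if the effect size is only 5% of a standard deviation".

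On numbers of practices, section 9.2.1 states: "We anticipate 32 out of 39 teams from USMM to meet eligibility and 26 out of 28 practices for Ochsner". Section 9.2 itself uses at least 30 for USMM. The Ochsner patient count is built from "10,000 members in Ochsner with approximately 10 percent of members diagnosed with dementia in 2019, we should have" 500 per group. The Précis gives the combined total: "We anticipate a total of approximately 5,000 patients will be included in this final analysis across both ACOs".

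Neither the protocol nor its statistical section gives a within-patient correlation, a practice ICC, a design-effect formula or a source for the 20%.

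**The concern.** Repeated quarters on one patient, and patients sharing a practice, each carry less information than independent observations. The plan describes the first correlation as significant and the second as modest, yet takes off one fifth for both together. After the deduction each patient still counts as 1,600/500 = 3.2 independent observations out of a possible 4, which is close to independence between quarters. The MPR definition in section 9.4.1 points the other way, because surplus supply from one quarter is carried into the next.

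The same 20% is applied to both ACOs, although practices average about 38 patients in Ochsner and about 125 in USMM. A common practice ICC would not cost the two the same.

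What is at stake is interpretation. A non-significant Ochsner result would be read as coming from a comparison with 80% power for the hypothesised effect, when the plan's own description does not support that figure.

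**Working it through.** **Inputs from the documents (sections 9.2 and 9.2.1).** Patients per group: 500 (Ochsner), 2,000 (USMM). Four quarters per patient. Practices per arm: 26/2 = 13 and 32/2 = 16, so patients per practice m = 500/13 = 38.5 and 2,000/16 = 125. Effects of 0.10 and 0.05 SD; 5% significance. Sidedness is not stated, but two-sided reproduces the plan's figures.

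**Step 1: the plan's own powers.** Power = Φ(d√(n/2) − 1.96), with n the effective observations per group.
- Ochsner, n = 1,600, d = 0.10: √800 = 28.28; Φ(2.828 − 1.96) = 80.7%.
- USMM, n = 6,400, d = 0.05: √3,200 = 56.57; Φ(2.828 − 1.96) = 80.7%.
- USMM, n = 6,400, d = 0.10: 99.99%.

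The arithmetic after the deduction is right. The fault lies in the 20%.

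**Step 2: what a 20% loss allows.** The design effect is 1/0.8 = 1.25. With rho the correlation between two quarters of one patient, and ICC the correlation between observations on different patients in one practice,

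design effect = 1 + 3·rho + 4(m − 1)·ICC.

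- With ICC = 0: rho ≤ 0.25/3 = 0.083.
- With no within-patient correlation beyond the practice's own (rho = ICC): ICC ≤ 0.25/(153.8 − 1) = 0.0016 in Ochsner and 0.25/(500 − 1) = 0.0005 in USMM.

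This step uses no outside values.

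**Step 3: power under assumed correlations.** The documents give no rho or ICC, so every value below is an assumption. Effective n = 4 × patients / design effect. At ICC 0 the design effects for rho 0.3, 0.5 and 0.8 are 1.9, 2.5 and 3.4, which are losses of 47%, 60% and 71%. Ochsner effective n is then 2,000/1.9 = 1,053, 2,000/2.5 = 800 and 2,000/3.4 = 588. USMM is 4,211, 3,200 and 2,353. Pooled effective n is the sum of the two.

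| ICC | rho | Ochsner, 0.10 SD (stated 80%) | USMM, 0.05 SD (stated 80%) | USMM, 0.10 SD (stated almost 100%) | Pooled, 0.10 SD |
|---|---|---|---|---|---|
| 0 | 0.3 | 63% | 63% | 99.6% | 99.9% |
| 0 | 0.5 | 52% | 52% | 98% | 99% |
| 0 | 0.8 | 40% | 40% | 93% | 97% |
| 0.005 | 0.5 | 42% | 29% | 81% | 92% |
| 0.005 | 0.8 | 34% | 26% | 74% | 86% |
| 0.01 | 0.5 | 35% | 21% | 64% | 80% |
| 0.01 | 0.8 | 30% | 19% | 59% | 74% |

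Using 15 USMM practices per arm, as section 9.2 implies, changes the USMM figures by at most 2 points.

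**Step 4: effect detectable with 80% power,** (1.96 + 0.842)√(2/n), for rho 0.5 to 0.8. At ICC 0: 0.14–0.16 SD in Ochsner, 0.07–0.08 in USMM, 0.06–0.07 pooled. At ICC 0.01: 0.18–0.20, 0.12–0.13 and 0.10–0.11.

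**Step 5: the Ochsner count.** 10,000 × 0.10 / 2 = 500 exactly. That leaves no stated allowance for taking 26 of 28 practices, for the visit requirement, for metastatic cancer and hospice exclusions, or for the coverage rule in section 4.1: "They have continuous coverage in Medicare Parts A, B and D and no months of Part C (Medicare Advantage".

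**The case against.** **Baseline adjustment.** Adjusting for pre-intervention MPR could recover precision. At ICC 0 and rho 0.7, one baseline quarter gives 2,000/(1 + 3 × 0.7 − 4 × 0.7²) = 1,754 effective observations in Ochsner, above the stated 1,600. The covariate list in section 9.4.2 is not exhaustive, and modelling the randomization strata could reduce the residual ICC. This stands as a possibility, but it does not support the text. The plan names only age and sex as key covariates, section 9.2 does not rely on baseline adjustment, and the gain depends on rho: at 0.5 the same formula gives 1,333 and 73% power.

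**USMM may exceed its floor.** 39,000 × 20% = 7,800 members with dementia; × 30/39 practices = 6,000, or 3,000 per arm before eligibility filters. At 3,000 and ICC 0, power at 0.05 SD is 80%, 69% and 56% for rho 0.3, 0.5 and 0.8. This softens the USMM figures, but the stated power uses 6,400, and an ICC of only 0.001 brings the best of these to 66%.

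**Consequences are limited.** Section 9.1 calls this a demonstration project. The sample is every eligible beneficiary in two fixed ACOs, and the current version describes a trial already under way, so a correction would not alter enrolment. The hypothesis is 0.10 SD, where USMM and the pooled data do far better than Ochsner, and the 0.05 SD claim is a side remark. All of this is fair and bears on how serious the point is. It does not make the two 80% statements correct.

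**The Ochsner count** is given as approximate, and the loss to filters is unknown. It is therefore a secondary point with no effect on power quantified here.

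**Conclusion.** The concern holds. The 20% deduction contradicts the plan's own description of the correlations, and this follows from the four quarters per patient alone. The 80% powers for Ochsner at 0.10 SD and USMM at 0.05 SD are therefore unsupported. It is an unsupported assumption, not an error in the power formula.

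How far power falls depends on correlations that the documents do not give. Over the assumed range of rho 0.3 to 0.8, both figures are 40–63% before any practice clustering, and lower with it. The almost-100% claim for USMM at 0.10 SD largely survives within-patient correlation (93% or more at ICC 0) and depends mainly on the practice ICC. The calculations assume equal practice sizes, an unadjusted comparison and a normal approximation. Unequal practice sizes and only 13 to 16 practices per arm would lower power somewhat; baseline adjustment, if specified, would raise it.

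**What to change.** In section 9.2, replace the 20% with a design effect built from quarters per patient, patients per practice and number of practices. Estimate the within-patient correlation and the practice ICC from the 2019–2020 claims already used to select clinics, or show a range if an estimate is not available. If the power is meant to rely on baseline MPR or the randomization strata, name them in the analysis model and in the power text.

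Restate effective sample size, power and detectable effect for each ACO, and add the pooled figure for the approximately 5,000 patients in the Précis. Use one USMM practice count (30 or 32) throughout. Support the Ochsner 500 with a count of eligible patients, or label it as approximate and before filters. Whether a pooled, ACO-stratified test becomes primary is for the sponsor to decide.

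The cost is protocol wording and a small analysis of claims already held. Restating the figures needs no further patients, but it would not restore the power claimed for Ochsner, and the published power is likely to look less favourable.

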### Objectives

The primary objective is to assess the effectiveness of training a clinician to be a 'value champion' within their clinical setting to decrease the use of three classes of potentially inappropriate prescription medications (PIMs) among people living with dementia.

(PLWD) Secondary objectives include determining if the intervention is associated with a reduction in emergency department (ED) visits or hospitalizations due to a fall, and examining five implementation outcomes: appropriateness, feasibility, fidelity, penetration, and equity.

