## **1 STUDY OBJECTIVES**

### **1.1 Primary Objective**

The Primary Outcome is medication possession rates (MPR) per quarter, for any of the 3 classes of potentially inappropriate medications. Our hypothesis is that for each medication class, the intervention will produce clinically relevant decreases in mean possession rates of 10% of a standard deviation in patients seen in intervention clinics compared to those who are seen in control group clinics.

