#### Primary & Secondary Outcomes by Specific Aim:

Specific Aim #1: The primary outcome for this study will be medication possession rates (MPR) per quarter, for the 3 therapeutic classes of PIMs - antipsychotics, benzodiazepines, and hypoglycemics using currently available Medicare claims data from each participating ACO. These beneficiary-level measures are calculated as quotients with denominator equal to the length of the quarter and the numerators equal to the days supply for prescriptions within the class filled during the quarter, plus excess days-supply from the previous period minus excess days-supply remaining at the end. Unlike many studies using medication possession rates to exam adherence, we are interested in reducing, not increasing, the percent of days covered.

Specific Aim #2: As a secondary outcome, we will also assess the incidence of falls during the study window. Falls are difficult to monitor using claims data, but Min and colleagues have developed a method that IAC and Brandeis staff (Co-Investigator [name]) have helped test for ICD-10. We will use the most conservative definition that looks for the presence of fall 'reason for visit' code on ED, ambulatory, or inpatient visit as indicated by a clinician bill (Part B).

Specific Aim #3: The five important implementation outcomes: appropriateness, fidelity, feasibility, and penetration will be assessed by analysis of interviews conducted with a group (approximately 8) of clinician value champions who have completed the webinar training.

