Duration of Enrollment and Follow-up: Using Medicare claims data for our primary outcome, with a follow-up period of one year after completion of the 6-months of value champion training, and with medication possession rates calculated per patient each quarter, we will have approximately 4 MPR observations per patient or 8,000 observations per group for USMM analyses and 2,000 per group for Ochsner.

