### 9.4 Outcomes

#### 9.4.1 Primary outcome

The primary outcome for this study (Specific Aim #1) will be medication possession rates (MPR) per quarter, for the 3 therapeutic classes of medications - antipsychotics, benzodiazepines, and hypoglycemics - that are considered low-value for beneficiaries with dementia. These beneficiary-level measures are calculated as quotients with denominator equal to the length of the quarter and the numerators equal to the days supply for prescriptions within the class filled during the quarter, plus excess days-supply from the previous period minus excess days-supply remaining at the end. Unlike many studies using medication possession rates to exam adherence, we are interested in reducing, not increasing, the percent of days covered. As a first choice, we will try to use originally-valued MPR variables in regression modeling, but if they don't reflect adequate

fit, we will transform them or possibly convert them to ordinal variables instead. For example, Benner and colleagues in their study of statin adherence defined non-adherence as MPRs within 0-20 percent, low-adherent as between 21-79 percent and high adherence as 80 percent or higher. In addition to MPRs, we will also calculate and analyze the number of 30-day prescriptions per time-period for each beneficiary in the study.

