## **10 DATA COLLECTION AND QUALITY ASSURANCE**

### **10.1 Data Collection Forms**

We have two primary data sources: the 100% Medicare claims files from each ACO, and interviews with clinicians conducted by staff at KPHRI and Brandeis. . Secondary data from Medicare Part D pharmacy claims data will provide us with our primary outcome data: cumulative exposure to any of the PIMs among an inception cohort of PLWD. In addition, Medicare claims data will be used for the third exploratory aim: rates of ED visits or admissions for a fall. This data will be identified and collected by the study programmer / analyst at AIC.

The Clinician interviews will provide us with the data we need for our implementation outcomes. A interview protocol is submitted for review. Data Management

Clinical Site Responsibilities: The two participating ACO organizations have Data Use Agreements with the Institute for Accountable Care, to access their 100% Medicare Claims data for purposes of the secondary data analyses for Specific Aims #1 & 2.

The Institute for Accountable Care will be responsible for data management of the secondary Medicare claims data. Their programmers will create a de-identified analytic file for Drs. [name] and [name] to use to test hypotheses for Aims #1 & 2.

The clinician interviews will be conducted and recorded by staff at KPHRI and Brandeis University. The recorded interviews will be transcribed, and the transcriptions will be analyzed by staff at both Brandeis and KPHRI.

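### Three primary medication classes in two ACOs are each tested at 5%, with no rule for which results decide success and no control of error across them

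*Combined protocol and SAP*

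**What the plan says.** **Objective and outcome.** The Précis (Objectives) sets one effectiveness objective: "to decrease the use of three classes of potentially inappropriate prescription medications (PIMs) among people living with dementia". Section 1.1 reads "The Primary Outcome is medication possession rates (MPR) per quarter, for any of the 3 classes of potentially inappropriate medications". Its next sentence, repeated in sections 9.1 and 9.2, states the hypothesis as a decrease of 0.10 SD for *each* class. The favourable direction is explicit: "we are interested in reducing, not increasing, the percent of days covered" (section 3).

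**Significance level.** Section 9.2 sets power for one class in one ACO: "If the effect size is this large for a medication class and using a 5% level of significance, our Ochsner sample" is given 80% power, "while our larger USMM sample (with effective size of at least 6,400 per group) will have almost 100% power". The 5% is not divided, and its sidedness is not stated.

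**Level of analysis.** Section 3 (Duration of Enrollment and Follow-up) counts "8,000 observations per group for USMM analyses and 2,000 per group for Ochsner", which suggests separate analyses. The Précis (Sample Size and Population) expects about 5,000 patients in a single final analysis covering both ACOs. The model descriptions in sections 9.1 and 9.5 do not settle it.

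**Outcome scale.** Section 9.4.1 prefers untransformed MPR, but if the fit is inadequate, "we will transform them or possibly convert them to ordinal variables instead". No fit criterion is given. Prescription counts are analysed in addition, and section 9.5 explores several time specifications.

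**Error control.** I found no success rule, lead class, testing order or multiplicity adjustment. Section 9.3 covers only the absence of interim analyses.

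**The concern.** A single effectiveness question may be answered by three results (classes, ACOs pooled) or six (classes by ACO). The plan does not say how to read them together. A decrease in one class in one ACO could be reported as success under one reading and failure under another, and the choice could be made after the results are known. If any one significant decrease counted, the 5% level would not hold for the overall conclusion.

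Two other conflicts affect what is estimated and in whom:

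- Section 10.1 describes the primary outcome data as "cumulative exposure to any of the PIMs among an inception cohort of PLWD". Sections 1.1, 3, 9.1 and 9.4.1 use quarterly MPR per class, and section 9.5 expects both incident and prevalent dementia.
- The Précis and section 9.1 fix patient eligibility before the intervention starts. Sections 3 (Study Population), 4.1 and 6.2.1 (Screening) fix it during the intervention year.

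**Working it through.** **1. The plan's power figures.** Two-sided normal test, SE = √(2/n) in SD units, using the plan's effective n per group.

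- Ochsner, n = 1,600, 0.10 SD: 0.10 × √800 = 2.828; Φ(2.828 − 1.960) = 80.7%.
- USMM, n = 6,400, 0.10 SD: 99.99%.
- USMM, n = 6,400, 0.05 SD: 80.7%.

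These match the stated 80%, almost 100% and 80%. A one-sided 5% test would give 88.2% for the first and third. I therefore take the 5% as two-sided, so a false *favourable* result has probability 2.5% per test. This is an inference; the plan does not say it.

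**2. Chance of at least one false decrease if any one counts, with no true effect.**

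- Independent tests: 1 − 0.975³ = 7.3%; 1 − 0.975⁶ = 14.1%.
- Correlated classes (equal correlation r, assumed because the plan gives none): p₃ = 1 − ∫ φ(x) Φ((1.96 − √r·x)/√(1 − r))³ dx. The ACOs have different clinics and patients and are taken as independent, so p₆ = 1 − (1 − p₃)².

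| r | 3 tests, pooled | 6 tests, per ACO |
|---|---|---|
| 0 | 7.3% | 14.1% |
| 0.5 | 6.3% | 12.2% |
| 0.8 | 4.9% | 9.6% |
| 0.9 | 4.2% | 8.2% |

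The reference is 2.5%. If the 5% were one-sided, the independent figures would be 1 − 0.95³ = 14.3% and 1 − 0.95⁶ = 26.5%, against 5%. If all three classes had to succeed in a pooled analysis, the chance would be at most 2.5%.

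**3. Price of Holm on the plan's own effective sizes.** The smallest P value must reach 0.05/3 = 0.0167 (critical value 2.394), or 0.05/6 = 0.0083 across six tests.

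- Pooled, n = 6,400 + 1,600 = 8,000: above 99.9% at 0.10 SD; at 0.05 SD it falls from 89% to 78%.
- Ochsner alone at 0.10 SD: from 81% to 67% (0.0167) or 58% (0.0083).

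**4. The same price under explicit clustering.** The pooled 8,000 counts four quarters per patient with a 20% reduction in all. As a check, take the section 9.2 counts: 30 USMM practices (15 per arm, 2,000 patients) and 26 Ochsner practices (13 per arm, 500 patients). Assume equal practice sizes within ACO, no baseline adjustment, quarter-to-quarter correlation ρ of 0.5 to 0.8 and practice ICC of 0 to 0.01. The documents give no correlations.

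Variance of an arm mean in one ACO: V = ICC/k + (ρ − ICC)/n + (1 − ρ)/(4n), with k practices and n patients per arm. The pooled effective n, stratified by ACO, is 1/V(USMM) + 1/V(Ochsner).

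Example, ICC 0.005 and ρ 0.5:

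- USMM: 0.005/15 + 0.495/2,000 + 0.5/8,000 = 0.000643, so 1,554.
- Ochsner: 0.005/13 + 0.495/500 + 0.5/2,000 = 0.001625, so 615.
- Total about 2,170. Power at 0.0167: Φ(0.10 × √1,085 − 2.394) = Φ(0.900) = 82%.

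| ICC | Effective n per group (ρ 0.8 to 0.5) | Power at 0.05 | Power at 0.0167 |
|---|---|---|---|
| 0 | 2,941–4,000 | 97–99% | 93–98% |
| 0.005 | 1,805–2,170 | 85–91% | 73–82% |
| 0.01 | 1,329–1,527 | 73–79% | 57–64% |

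For 80% power at 0.10 SD the required effective n is 1,570 at 0.05 and 2,094 at 0.0167.

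**The case against.** The strongest reply is that the plan states its hypothesis for each class, three times. That fits three separate claims or one all-three claim. An all-three rule does not inflate error, and three separately reported class claims at 5% could be defended if the ACOs are pooled. The Précis wording on a final analysis across both ACOs supports pooling. All of this stands, and it is why the error figures are conditional. But a hypothesis for each class is an expectation, not a decision rule, and the ACO-by-ACO power statement points away from pooling.

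A reader might infer from the word *any* in section 1.1 that one significant class suffices. The documents do not support that: the word describes which drugs are measured, and the next sentence refers to each class. Nor do they establish that six tests are planned.

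Some of the hierarchy is already there. Untransformed MPR comes first, the treatment indicator is the key variable, prescription counts are additional and time interactions are exploratory. What is missing is the fit criterion and a statement that the alternatives cannot decide success.

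Section 9.1 calls the study a demonstration project. That lowers the stakes, but the same section states the effectiveness hypothesis and section 9.2 powers it.

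**Conclusion.** The gap is real and should be closed: the plan has no success rule, no settled level of analysis and no error control across three to six primary results. If any one decrease counted, the false-favourable risk would be 4.9% to 7.3% pooled or 9.6% to 14.1% per ACO, against 2.5%. These figures rest on the any-one reading, the inferred two-sided test, class correlation between 0.8 and 0, and independent ACOs. They do not show that the plan as a whole breaches 5%, because other readings consistent with the text do not.

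It would also be tempting to call the Holm correction nearly free because pooled power stays above 99.9%. That holds only if 8,000 effective observations per group are real; a practice ICC of 0.005 to 0.01 would bring power to about 57% to 82%.

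On eligibility, the intervention-year wording selects patients on visits and claims that occur after randomisation, so it can change who is analysed in each arm.

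**What to change.** Amend the protocol and date the amendment before anyone sees outcomes by arm. Timing matters because sections 6.2.1 and 11.2 show that the study is under way.

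1. Make one pooled analysis of untransformed quarterly MPR per class primary, stratified by ACO, with ACO-specific results secondary. Say that this changes the level powered in section 9.2.
2. State the rule: either Holm across the three classes at overall 5%, or all three classes significant at 5%. If ACO-specific tests remain primary, apply Holm across all six.
3. Keep transformed or ordinal MPR, prescription counts and time interactions secondary, and give the fit criterion in advance.
4. Separately, correct section 10.1 to match the quarterly per-class outcome, and use the pre-intervention eligibility window of the Précis and section 9.1 throughout.

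The cost is an amendment with IRB review (section 11.1) and no new data, since outcomes come from existing claims evaluated in months 18–24 (section 6.1). Holm costs the power shown above. The all-three rule keeps 5% per class but makes overall success harder: at ICC 0.005, with independent classes, the chance that all three succeed at 0.10 SD is 0.852³ = 62% to 0.909³ = 75%, and higher if the classes are positively correlated. The sponsor should choose with these ranges in view.
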